### **3.4 Allocation concealment, blinding and order of analysis**

#### **3.4.1 Allocation concealment**

As the groups are randomised using a computer-generated block randomisation provided by a third party (the Clinical Research Unit at the Faculty of Medicine and Health Sciences at the Norwegian University of Science and Technology), the research team will not be able to influence the randomization process in any way and the allocation sequence is hence concealed until the moment of assignment.

#### **3.4.2 Blinded statistician**

As we randomize 2:1 blinding is a challenge. Therefore, we will write and publish the syntax for the main analyses before the analyses are performed. The researcher performing the analyses will present the results graphically without group labels, group size, and confident intervals to the rest of the project group. A written interpretation of the results will then be conducted by the project group before the group information is revealed.

## 4. Presentation of study population

### 4.1 Screening data, eligibility and recruitment

See section 2.1 for flowchart over participants in the study (figure 1).

### 4.2 Withdrawal / follow-up

We will describe how many participants drop out during the study and reason for this if available (due to ethical consent there is no obligation for provide a reason for dropping out). If participants do not answer the questionnaire, they will be registered as ‘lost to follow-up’. If participants withdraw their consent, they will be excluded unless their data has already been included in analyses or published.

### 4.3 Baseline patient characteristics

Descriptive statistics will be presented stratified by group allocation. Descriptive statistics will include age, gender, education, work status, medical benefits, pain intensity, anxiety and depression, sleep and pain medication, fatigue, health-related quality of life, physical activity, physical function, and insomnia severity. Categorical and binary variables will be presented as counts and percentages, continuous variables will be presented as means and standard deviation (SD) or medians and interquartile range (IQR), as appropriate.

## 5. Analysis

### 5.1 Outcome definitions

#### 5.1.1 Primary outcome

The primary outcome is insomnia measured by ISI at three months follow-up. ISI is the gold standard self-report measure of insomnia severity in clinical practice, consisting of seven items assessing symptoms of insomnia such as difficulty falling or staying asleep, satisfaction with sleep, and degree of impairment with daytime functioning. The total score of ISI ranges from 0 to 28. ISI has been validated and has proven sensitive to therapeutic changes [2]. For the primary analyses ISI will be included as a continuous variable. See table in 2.7.2 for details concerning measurement time.

#### 5.1.2 Secondary outcomes

- 1) Difference in the proportion of participants that achieves an 8-point improvement on ISI between the intervention group and the control group. This is in accordance with the literature suggesting an improvement of the ISI score  $\geq 8$  points is a meaningful improvement, indicating that the intervention has a positive impact on the individual’s sleep [2].
- 2) The effect of the intervention on
  - a. pain intensity measured using a visual analogue scale from 0 to 100.
  - b. fatigue measured using a visual analogue scale from 0 to 100.
  - c. health-related quality of life measured by EQ-5D.
  - d. physical function measured by PSFS.
  - e. physical activity measured by three questions about frequency, duration and intensity of physical activity per week

## **STATISTICAL ANALYSIS PLAN for “Digital sleep therapy in patients with Musculoskeletal complaints and insomnia”**

The above listed outcomes will be analyzed for 3-, 6-, and 12 months of follow-up, with 3 months being the main assessment point.

In additional publications, we will investigate the long-term effects (12 months) of dCBT-I on sickness absence and use of prescribed sleep and pain medication.

- 1) Work outcomes: 1) Difference between the two groups in total number of sickness absence during 12 months of follow-up and 2) probability of working (i.e., not receiving medical benefits) each month during 12 months of follow-up. Based on registry data from NAV.
- 2) Difference in the proportion of participants that obtain prescriptions for sleep and pain medication between two groups during 12 months of follow-up. Based on registry data from NPD.

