#### 1.1 Purpose and scope of the statistical analysis plan

This document details the proposed analyses of the main paper reporting results from the study *“Digital sleep therapy in patients with musculoskeletal complaints and insomnia referred to inpatient multimodal pain rehabilitation”*. Any deviations from the analyses outlined in this SAP will be described and justified in the final report of the trial, including the inclusion of any analyses suggested by journal editors and referees. Modifications will be carefully considered and, as far as possible, follow the broad principles set out here.

First and foremost, this SAP describes the analysis of the primary and secondary outcomes. Subsequent exploratory analyses are also expected to follow the broad principles of this SAP but are not described in detail here.

The details presented here shall not prohibit accepted practices, such as data transformation prior to analysis. When possible, such data management and modelling decisions will be undertaken prior to revealing the treatment allocation. The final analysis strategy will be available on request when the papers are submitted.

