## **5.2 Analysis of primary outcome**

We will use linear mixed model analysis to estimate mean difference in ISI between the two groups at 3, 6 and 12 months of follow-up, with the primary outcome measurement at 3 months. The model will include participant ID as a random effect and time, time–group interaction and baseline covariates as fixed effects. Of baseline covariates we will include age, sex, and education. Determination of possible categorizing of the covariates will be done before unblinding and published in an updated version of this SAP.

The assumption of normally distributed residuals will be assessed by visual inspection of histograms and Normal Q-Q plots. Model assumptions for mixed models will be checked: residuals (approximately) normally distributed and homogeneity of residual variance (homoscedasticity).

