## 5.3 Analysis of secondary outcomes

For binary secondary outcomes (e.g., clinically relevant change in ISI, minimal important change in PSFS), we will use a generalized estimated equation logistic model to estimate the odds ratio (OR) for achieving at least an 8-point improvement in ISI score. In these analyses, we will assume an exchangeable correlation structure and a robust variance estimator. For the other secondary outcomes, a mixed linear regression model will be used.

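### The SAP specifies no adjustment for baseline work or benefit status in the registry work outcomes, so it gives up precision that a variable already collected could supply

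*SAP*

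**What the plan says.** SAP 1.3.2 makes sickness absence part of secondary objective 3, subject to successful register linkage. SAP 5.1.2 defines two work outcomes: "Difference between the two groups in total number of sickness absence during 12 months of follow-up" and "probability of working (i.e., not receiving medical benefits) each month during 12 months of follow-up". It places them outside the main paper: "In additional publications, we will investigate the long-term effects (12 months) of dCBT-I on sickness absence".

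On scope, SAP 1.1 says two things: "This document details the proposed analyses of the main paper reporting results from the study", but also "this SAP describes the analysis of the primary and secondary outcomes".

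On modelling, SAP 5.2 says for the ISI model: "Of baseline covariates we will include age, sex, and education". SAP 5.3 gives binary secondary outcomes a GEE logistic model with an odds ratio, and then: "For the other secondary outcomes, a mixed linear regression model will be used". It lists no covariates for either type.

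On baseline data, Table 1 lists work status among the enrolment assessments, and SAP 2.7.1 puts the baseline questionnaire before randomisation. SAP 4.3 uses the information for description: "Descriptive statistics will include age, gender, education, work status, medical benefits". No section names work status or benefits as an adjustment variable.

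**The concern.** The registry outcomes count sick leave, work assessment allowance and disability pension (SAP 2.7.1). All three can run on from before entry, so benefit status at entry is plausibly a much stronger predictor of the following year than age, sex or education. ISI, pain, fatigue, EQ-5D and PSFS each have a baseline measurement on their own scale. The registry extract is described only for the 12 months after rehabilitation, so the work outcomes have no baseline value in their own series. Recorded work status or benefits is the natural substitute.

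Randomisation is by rehabilitation group, with few and small groups. Arms will often differ by chance in the share already on benefits, and that difference adds noise to the work comparison. If the covariate is not chosen in advance, it may be chosen after the main results are known, on outcomes that are likely to be sensitive to it.

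**Working it through.** **1. The plan's own figure.** The only power figure is for ISI (SAP 2.3): 15 clusters at 2:1, about 5 per cluster, SD 4, difference 4, ICC 0.2, CV of cluster size 0.7, two-sided 5%, power 80%.
- Design effect = [1 + (m−1)·ICC]/RE, with RE = 1 − CV²·λ(1−λ) and λ = m/(m + (1−ICC)/ICC) = 5/9 = 0.556.
- RE = 1 − 0.49 × 0.556 × 0.444 = 0.879, so the design effect is 1.8/0.879 = 2.05.
- SE = 4·√[2.05 × (1/50 + 1/25)] = 1.40, and power = Φ(4/1.40 − 1.96) = 81%.

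The 80% is reproduced. It says nothing about the work outcomes, for which the SAP gives no SD, rate or correlation.

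**2. Chance imbalance in baseline benefit status.** From the SAP: 21 clusters at 2:1, so 14 v 7, and about 5 per cluster, so 70 v 35. Assumed: share on benefits p = 50%, and an ICC for that share between 0 and 0.2 (0.2 is the SAP's planning value for ISI, borrowed here).
- SD = √[p(1−p) × DE × (1/70 + 1/35)].
- ICC 0: √(0.25 × 0.0429) = 10.4 points.
- ICC 0.2, CV 0.7, with the cruder DE = 1 + (1.49 × 5 − 1) × 0.2 = 2.29: √(0.25 × 2.29 × 0.0429) = 15.7 points.
- For p from 30 to 70%, the SD is 9.5 to 15.7 points and the chance of an imbalance of at least 10 points is 0.29 to 0.52. With 15 clusters (50 v 25) the SD is 11.2 to 18.5 points.

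**3. What the imbalance does to an unadjusted estimate (assumed rates).**
- Monthly outcome: if 20% of those on benefits at entry and 80% of the others are benefit-free later, the gap is 0.6. A 1-SD imbalance moves the estimate by 0.6 × 10.4 = 6 points to 0.6 × 15.7 = 9 points.
- Absence days: if those on benefits at entry have 60 to 180 more days in the year, a 10-point imbalance moves the difference by 6 to 18 days.

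**4. Precision on a difference scale.** The SE is multiplied by √(1 − R²).
- R² = 0.25: 0.87, an interval 13% narrower, worth 1/0.75 − 1 = 33% more participants.
- R² = 0.50: 0.71, an interval 29% narrower, worth 1/0.50 − 1 = 100% more participants.
- The rates in step 3 give R² = 0.25 × 0.6²/0.25 = 0.36. With no effect and independent observations in one month, the SE of the risk difference falls from √(0.25 × 0.0429) = 0.104 to √(0.16 × 0.0429) = 0.083, a factor of 0.80.
- A correlation of 0.3 (R² = 0.09) gives a factor of only 0.95.

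**5. The odds-ratio scale.** On the same inputs, the SE of the log odds ratio is √(1/17.5 + 1/8.75) = 0.41 unadjusted (70 × 0.25 = 17.5; 35 × 0.25 = 8.75). Adjusted, it is √(1/11.2 + 1/5.6) = 0.52 (70 × 0.16 = 11.2; 35 × 0.16 = 5.6). The SE rises. Power can still improve because the conditional odds ratio lies further from 1, but the narrowing in step 4 does not carry over.

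**The case against.** A reader might infer that the SAP has decided to compare the work outcomes unadjusted. It has not. The quoted definition stands under outcome definitions and says what is compared, not how; 5.3 lists no covariates for any secondary outcome. The supportable statement is that no such adjustment is specified. Even if the ISI covariates were carried over, work status would still be absent.

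A reader might also infer bias, or that any work effect could be a mere artefact of who was on benefits at entry. The documents do not support that. Randomisation keeps the unadjusted comparison unbiased, and an interval that respects the clustering already allows for chance imbalance. The shifts in step 3 of the working are ordinary sampling error in a single trial, not a systematic error.

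The outcomes are deferred to other publications and conditional on linkage, and SAP 1.1 limits the document to the main paper. This lowers the urgency. It is not a full answer, because the same section claims the secondary outcomes and these are listed among them. SAP 1.1 also plans modelling decisions before allocation is revealed where possible, so there is still room to settle the covariate.

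Two further objections stand. The size rests on assumed rates. And with about 35 controls in 7 groups, a category such as disability pension could be sparse, with members almost never benefit-free, which risks separation in a logistic model.

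**Conclusion.** The point holds as a worthwhile improvement in precision; the SAP contains no error or contradiction here. The plan leaves out of its named covariates a pre-randomisation variable that is likely to be strongly prognostic for both work outcomes.

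Under assumed R² values of 0.25 to 0.50, adjustment would narrow the interval for a mean or risk difference by about 13 to 29%. With weaker prognosis (R² 0.09) the gain is about 5%. With clustering, the realised gain also depends on how much of the between-group variation baseline status explains. None of these inputs is in the SAP, so the size is indicative. It does not apply to the odds ratio that 5.3 would produce for the monthly outcome.

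**What to change.** In SAP 5.3, or in the updated SAP that 5.2 promises on covariate categories, state that both work-outcome models include baseline work status or benefit status as a fixed covariate alongside age, sex and education. Fix the categories blind to allocation and give a rule for merging sparse levels. For the monthly binary outcome, report a standardised (marginal) risk difference from the adjusted model, so that the gain appears on an interpretable scale. Say in the same place how these models handle rehabilitation group.

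State the source of the covariate. The registry extract is described only for the period after rehabilitation, so the baseline questionnaire or the baseline benefits record would have to supply it.

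The cost is a few sentences and one or two parameters, with no new data. The risk is sparse categories in the smaller arm, which the merging rule addresses.

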### **1.3.2 Secondary and exploratory objectives**

Secondary objectives:

- 1) Examine the difference in the proportion of participants that achieves an 8-point improvement in their ISI-score between inpatient multidisciplinary rehabilitation + dCBT-I (intervention group) and inpatient multidisciplinary rehabilitation only (control group), 3-, 6-, and 12 months after end of rehabilitation.
- 2) Evaluate the effectiveness of the intervention on pain intensity, fatigue, health-related quality of life, physical function, and physical activity at 3-, 6-, and 12 months after end of rehabilitation.
- 3) Evaluate the long-term effectiveness of the intervention on sickness absence and use of prescribed sleep and pain medication during 12 months of follow-up after rehabilitation (this will be done if successful register linkage within the time frame of the project).

If the data material allows it, it will be relevant to examine the following exploratory objectives:

- 4) Explore whether changes in pain intensity and fatigue mediate the effect of dCBT-I on insomnia severity.
- 5) Explore whether sex, age, symptoms of anxiety and depression, pain intensity and level of physical activity at baseline moderate the effect of dCBT-I on insomnia severity and secondary outcomes (pain intensity, health-related quality of life, sickness absence and use of prescription sleep and pain medication).

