#### **Questionnaires**

Self-reported web-based questionnaires are answered at five time points: at baseline (prior to randomization), 6 weeks (at the end of rehabilitation), at 3 months (primary outcome measurement), 6 months, and 12 months after end of rehabilitation.

In addition, diagnoses and use of medication at baseline will be available through the electronic patient records.

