#### **Registry Data**

Registry-based data will be obtained for 12 months of follow-up after rehabilitation from the Norwegian Prescription Database (NPD) and the National Insurance Administration (NAV). From NPD, we will obtain data on use of sleep and pain medications and assess the proportion of participants that obtain prescriptions of these medications during the follow-up. From NAV, we will obtain data on use of medical benefits (sick leave, work assessment allowance and disability pensions). Work participation outcomes will include both total number of days of sickness absence during 12 months follow-up and the probability of being at work (i.e., without medical benefits) each month during the same period.

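### The 12-month yes/no prescription outcome misses reductions in medication use that come after the first follow-up prescription; add a quarterly or monthly series adjusted for baseline use

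*SAP*

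**What the plan says.** Section 1.3.2 lists, among the secondary objectives, the long-term effect on "use of prescribed sleep and pain medication during 12 months of follow-up after rehabilitation", conditional on register linkage succeeding in time. Section 5.1.2 turns this into an outcome: "Difference in the proportion of participants that obtain prescriptions for sleep and pain medication between two groups during 12 months of follow-up". Section 2.7.1 (Registry Data) says the same of the prescription registry, namely that the plan is to "assess the proportion of participants that obtain prescriptions of these medications during the follow-up", and sets the extract window: "Registry-based data will be obtained for 12 months of follow-up after rehabilitation from the Norwegian Prescription Database (NPD"). No number of prescriptions, dispensed amount, sub-period or repeated measure is given for medication.

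The work outcome, listed beside it in 5.1.2, has both a 12-month total and a probability for each month.

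Medication before treatment comes from another source: "diagnoses and use of medication at baseline will be available through the electronic patient records" (2.7.1, Questionnaires; also Table 1). Section 4.3 includes it in the baseline description ("pain intensity, anxiety and depression, sleep and pain medication, fatigue, health-related quality of life"). It is not linked to the medication outcome. The only adjustment covariates the SAP names are for the primary model: "Of baseline covariates we will include age, sex, and education". Section 5.3 assigns binary secondary outcomes to a logistic GEE with exchangeable correlation and robust variance, and does not mention prior use.

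**The concern.** A yes/no over a whole year is settled by the first prescription. A participant supplied once in month 1 who then stops is indistinguishable from one supplied in all twelve months. A participant who uses less but still fills one prescription contributes nothing to the contrast. If better sleep leads to less medication gradually, much of that change falls after the answer is already fixed at yes. The trial could then report little difference in medication although use had diverged by the end of the year.

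The registry data can carry more information, since the SAP already plans a month-by-month analysis for the work outcome. Baseline medication use, a likely strong predictor of later prescriptions, is collected but left out of this analysis.

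**Working it through.** The SAP gives no rate, effect size or power for medication, so there is no stated figure to reproduce. Its only design calculation concerns the ISI score and has no bearing here.

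**Step 1: what the definition can register.** Suppose a fraction *e* of those who stop do so before any follow-up prescription. Only they move from yes to no, so the visible difference is the true stopping difference multiplied by *e*. As an illustration with assumed inputs, let 50% of intervention users and 10% of control users stop, with 30%, 50% or 70% of participants being users. The true difference at year end is 0.4 × 30%, 50% or 70% = 12, 20 or 28 points. The whole-year outcome shows:

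- *e* = 0: 0 points at all three rates
- *e* = 0.25: 3, 5 or 7 points
- *e* = 0.5: 6, 10 or 14 points

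**Step 2: dependence on the time of stopping.** Assumed inputs, none from the SAP:

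- *u*, share of users at entry: 0.6 or 0.8
- *m*, probability that a continuing user has a dispensing in a given month: 1/3 or 1/2, independent between months
- half of intervention users stop after month *k* of follow-up; no control user stops; there are no new users

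Whole-year yes, control: *u*[1 − (1−*m*)^12].

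Whole-year yes, intervention: *u*{0.5[1 − (1−*m*)^12] + 0.5[1 − (1−*m*)^*k*]}.

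Difference: 0.5*u*[(1−*m*)^*k* − (1−*m*)^12].

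Months 10-12, control: *u*[1 − (1−*m*)^3]. The intervention arm has half of that, so the difference is 0.5*u*[1 − (1−*m*)^3] for any of these *k*.

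Example, *u* = 0.6, *m* = 1/3, *k* = 3: 0.3 × (0.2963 − 0.0077) = 8.7 points. Last quarter: 0.3 × (1 − 0.2963) = 21.1 points.

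Differences in percentage points:

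| *u* | *m* | Whole year, stop by start (*k* = 0) | Whole year, stop after month 1 | Whole year, stop after month 3 | Months 10-12, all cases |
|---|---|---|---|---|---|
| 0.6 | 1/3 | 29.8 | 19.8 | 8.7 | 21.1 |
| 0.6 | 1/2 | 30.0 | 15.0 | 3.7 | 26.3 |
| 0.8 | 1/3 | 39.7 | 26.4 | 11.5 | 28.1 |
| 0.8 | 1/2 | 40.0 | 20.0 | 5.0 | 35.0 |

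The whole-year outcome is the more sensitive of the two when stopping precedes follow-up. It is somewhat to clearly less sensitive when stopping comes after month 1, and much less sensitive when it comes after month 3.

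**The case against.** The best defence is that the proportion with a prescription over a year is a simple registry endpoint and a fair reading of an objective about use during 12 months. The treatment is given alongside the inpatient stay and the registry window opens afterwards, so some users may already have stopped. In that case the table favours the SAP's outcome. This stands. It is why the whole-year proportion should stay, and why months 10-12 should not replace it: that would narrow the objective and set aside nine months of data.

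A reader might infer that the outcome cannot show a reduction at all, or that it mainly records who was a user at entry. The documents support neither. Even with stopping after month 3 a difference of 4-12 points remains, and the SAP gives no user rate from which the second claim could follow.

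A reader might also take the missing registry period before rehabilitation as a source of bias. It is not: allocation is randomised, so the comparison is valid without it. What is lost is precision, and the patient record already supplies a baseline measure.

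Finally, the outcome is meant for additional publications and depends on linkage, so nothing in the main paper rests on it. That limits the weight of the point. It does not remove it, because this is a listed secondary objective with a stated definition.

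**Conclusion.** The point holds as a matter of sensitivity, not validity. As defined, the outcome does not register stopping after the first follow-up prescription, or reduction without stopping. On the assumed inputs the whole-year contrast ranges from 30-40 points (stopping by the start of follow-up) through 15-26 (after month 1) to 4-12 (after month 3), against 21-35 points in months 10-12 throughout. These ranges rest on assumed user shares, dispensing frequency and stopping, with no stopping among controls and no new users. They show the direction and the dependence on timing, and do not predict this trial. Reading the outcome as at least one prescription is the natural sense of the text, although the SAP does not use the word any.

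A null whole-year result would still answer one version of the objective. It would leave open whether use had fallen later in the year. This is a worthwhile and cheap improvement, not an error that undermines the plan.

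**What to change.** In sections 2.7.1 (Registry Data) and 5.1.2:

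- Keep the 12-month proportion.
- Add, for sleep medication and pain medication separately, the proportion with a prescription in each quarter (or month) of follow-up. Analyse this as a repeated binary outcome with the logistic GEE of section 5.3, in line with the monthly work outcome.
- Report the last quarter alongside the whole-period contrast.
- Adjust these analyses for the baseline sleep and pain medication use already taken from the patient record.

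A registry look-back before rehabilitation is an optional gain in precision if the linkage approval allows it.

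The core change is SAP wording and uses data already planned, with no patient contact. Section 5.2 already foresees an updated SAP before unblinding, which could carry it. The price is a longer results table and more contrasts for a secondary outcome. One limit remains: a quarterly or monthly yes/no shows reduced use only where it leaves some periods without a prescription.

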**STATISTICAL ANALYSIS PLAN for “Digital sleep therapy in patients with Musculoskeletal complaints and insomnia”**

**2.7.2 Timing of endpoint assessments**

Table 1. Schedule for assessments

	Study period				
	Enrolment	Post-rehabilitation			
TIMEPOINT	Baseline	End of rehabilitation	3 months	6 months	12 months
ASSESSMENTS:					
Age					
Sex					
Education					
Work status					
Work satisfaction	X				
Work ability					
Work expectations					
Sleep and pain medication (from journal)					
Anxiety and depression (HSCL-25)	X	X			
Primary outcome					
Insomnia severity index (ISI)	X	X	X	X	X
Secondary outcomes					
Pain intensity	X	X	X	X	X
Fatigue	X	X	X	X	X
Health-related quality of life (EQ-5D)	X	X	X	X	X
Physical function (PSFS)	X	X	X	X	X
Physical activity (HUNT3 PA)	X		X	X	X
Registry data					
Sickness absence and disability pension					→
Sleep and pain medication					

HSCL-25: Hopkins Symptom Checklist, 25 questions. EQ-5D: European Quality of Life – 5 Dimensions. PSFS: Patient Specific Functional Scale. HUNT3 PA: Trøndelag Health Study (HUNT Study), physical activity questionnaire.

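### Baseline sleep and pain medication is collected but is not named as a covariate for the prescription outcome, which costs precision and leaves chance imbalance in existing users in the estimate

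*SAP*

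**What the plan says.** **Outcome.** Section 5.1.2, under the work planned for additional publications, lists the "Difference in the proportion of participants that obtain prescriptions for sleep and pain medication between two groups during 12 months of follow-up". Section 2.7.1 (Registry Data) says the same of the prescription register: the trial will "assess the proportion of participants that obtain prescriptions of these medications during the follow-up". Section 1.3.2 makes this part of secondary objective 3, conditional on register linkage succeeding in time.

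**Baseline value.** Section 2.7.1 (Questionnaires) states that "diagnoses and use of medication at baseline will be available through the electronic patient records". Table 1 in section 2.7.2 lists sleep and pain medication from the journal among the baseline items. The register itself supplies no baseline value as planned: "Registry-based data will be obtained for 12 months of follow-up after rehabilitation". The patient record is therefore the only baseline source that the SAP names.

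**Planned use of the baseline value.** Section 4.3 includes it in the baseline table: "Descriptive statistics will be presented stratified by group allocation". No other section uses it.

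**Model.** Section 5.3 gives binary secondary outcomes a logistic GEE and adds: "In these analyses, we will assume an exchangeable correlation structure and a robust variance estimator". It lists no covariates and does not name the clustering unit. The only adjustment covariates in the SAP belong to the ISI model in section 5.2: "Of baseline covariates we will include age, sex, and education".

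**The concern.** Medication use at entry is in effect the baseline measurement of this outcome, and it is likely to be among the strongest predictors of a later prescription. The trial randomises only 21 rehabilitation groups at 2:1, so the arms can easily differ in their share of existing users. Two things are at stake:

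- **Precision.** Variation explained by baseline use stays in the error term, and the interval is wider than it needs to be.
- **Interpretation of the one trial that is run.** An excess of existing users in one arm moves the observed difference in prescriptions, and the plan has no prespecified step to remove it. The baseline table will show any such imbalance by arm. If no rule is written beforehand, the choice to adjust could be made after that table has been seen.

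**Working it through.** **The plan's own figure.** The SAP gives no figure for prescriptions. Its only power statement (section 2.3) concerns ISI: 15 clusters of about 5, SD 4, difference 4, ICC 0.2, cluster-size CV up to 0.7, power 80%. The standard error is √(16 × DE × (1/25 + 1/50)). The design effect DE is 1.80 for equal clusters (power 86%), 2.05 with a relative-efficiency correction for unequal clusters (81%), and 1 + ((1 + 0.7²) × 5 − 1) × 0.2 = 2.29 with the usual CV correction (77%). The stated 80% is reproduced by the middle version. It does not bear on the prescription outcome.

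**Inputs from section 2.3.** 21 clusters × 5 participants = 105, split 2:1 into 70 and 35. So 1/35 + 1/70 = 0.0429.

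**Assumed inputs (not in the SAP).** Share of users at baseline p = 0.4 to 0.6. Probability of a later prescription a = 0.70 to 0.85 in users and b = 0.10 to 0.30 in non-users. Each medication class is taken separately.

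**Step 1: size of a chance imbalance in users.** SD = √(p(1 − p) × DE × 0.0429).

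- p = 0.5, no clustering: √(0.25 × 0.0429) = 0.104, or 10.4 points. The chance of an imbalance above 10 points is 33%.
- p = 0.5, DE = 2.29 (borrowing the ISI values of ICC and CV for medication use): 15.7 points. The chance of exceeding 10 points is 52%.
- p = 0.4 or 0.6, no clustering: 10.1 points.

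**Step 2: carry-over.** With no treatment effect, the unadjusted risk difference moves by (a − b) per unit of imbalance. The assumed ranges give 0.70 − 0.30 = 0.40 up to 0.85 − 0.10 = 0.75. A 10-point imbalance therefore shifts the estimate by 4 to 7.5 points.

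**Step 3: variance with and without adjustment, no clustering.** Let m = pa + (1 − p)b. The unadjusted variance per person is V = m(1 − m). The variance within baseline strata is W = pa(1 − a) + (1 − p)b(1 − b). The ratio is W/V, and each standard error is √(V or W, × 0.0429). For p = 0.4, a = 0.7, b = 0.3: m = 0.46, V = 0.46 × 0.54 = 0.2484, W = 0.4 × 0.21 + 0.6 × 0.21 = 0.2100, ratio 0.845.

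| p | a | b | V | W | W/V | SE unadjusted | SE adjusted | Variance cut |
|---|---|---|---|---|---|---|---|---|
| 0.4 | 0.70 | 0.30 | 0.2484 | 0.2100 | 0.845 | 0.103 | 0.095 | 15% |
| 0.4 | 0.85 | 0.20 | 0.2484 | 0.1470 | 0.592 | 0.103 | 0.079 | 41% |
| 0.4 | 0.80 | 0.10 | 0.2356 | 0.1180 | 0.501 | 0.100 | 0.071 | 50% |
| 0.5 | 0.85 | 0.10 | 0.2494 | 0.1088 | 0.436 | 0.103 | 0.068 | 56% |
| 0.9 | 0.70 | 0.30 | 0.2244 | 0.2100 | 0.936 | 0.098 | 0.095 | 6% |
| 0.9 | 0.85 | 0.10 | 0.1744 | 0.1238 | 0.710 | 0.086 | 0.073 | 29% |

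The last two rows lie outside the assumed range of p and show the gain shrinking when nearly everyone is a user. Fewer participants than 105 would widen the imbalance in step 1 but leave W/V unchanged.

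**Step 4: check by simulation.** In 20,000 null trials of 35 v 70 participants (p = 0.5, no clustering), with a/b of 0.7/0.3, 0.8/0.2 and 0.9/0.1, the unadjusted difference moved by 0.40, 0.61 and 0.80 per unit of imbalance. The adjusted one moved by about 0. The SDs fell from 0.104, 0.104 and 0.103 to 0.096, 0.083 and 0.062. Both estimators averaged zero.

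**The case against.** The strongest reply is that nothing here is invalid. Under randomisation the unadjusted contrast is unbiased, and a correctly computed interval already allows for chance imbalance. This stands. A reader might infer systematic bias or an inflated type I error from the missing covariate; the simulation shows neither, and nothing in the SAP implies either. The cost is precision, and error in the single trial that is run.

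A reader might also infer that the SAP has decided against adjustment. It has not. The sentence in section 5.1.2 is an outcome definition, and the ISI responder outcome, worded in the same way, is then given a model in section 5.3. The SAP is silent. But if the covariates of the primary model carried over, baseline medication would still not be among them.

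The scope objection also has force. Section 1.1 says that the document details the main paper, while this outcome goes to additional publications and depends on linkage. On the other side, section 1.1 also says that the SAP covers the secondary outcomes, and section 1.3.2 lists this as a secondary objective. That lowers the weight of the point without removing it.

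Section 5.3 is only a loose anchor, since its model is written around questionnaire outcomes and an odds ratio. The variance cut above applies to the risk difference. It should not be read across to the log odds ratio, where adjustment changes the quantity estimated and need not shrink the standard error.

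Finally, the SAP does not say how complete the record data are or how well they agree with the register. Poor agreement would reduce the gain.

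**Conclusion.** The point holds as a missed gain of low severity. The trial plans to hold the baseline version of this outcome, uses it only descriptively, and names it in no model. Under the assumed rates and without clustering, adjustment would reduce the variance of the risk difference by roughly 15% to 55%. It would also remove a shift of 4 to 7.5 points for each 10-point imbalance in existing users. If 90% were users at baseline, the cut would be between 6% and 29% for the two pairs of rates shown.

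The direction needs only that baseline use predicts later prescription; the size rests entirely on the assumed rates. Clustering would make imbalance larger, but its effect on the proportional gain has not been worked out here. The SAP sets no power for this outcome, so no loss of planned power can be claimed.

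**What to change.** Add to section 5.3:

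> *Each prescription outcome (sleep medication, pain medication) is analysed by a logistic model adjusted for use of the same medication class at baseline from the patient record, in addition to any covariates carried over from the primary model, with robust variance clustered on rehabilitation group and a small-sample correction. The treatment effect is reported as a standardised risk difference with its 95% confidence interval, alongside the odds ratio.*

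The clustering clause is essential. An ordinary logistic model that ignored rehabilitation group would ignore the unit of randomisation, and with 21 groups (about 14 v 7) an uncorrected robust variance is likely to be too small. The interval for the risk difference should use the same clustered variance.

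The cost is two sentences and no new data collection. Section 5.2 already promises an updated SAP before unblinding, so the text can go there. The one small downside is that the odds ratio becomes conditional on baseline use; the standardised risk difference addresses this and matches the outcome as section 5.1.2 defines it.
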